#### 4.4 Duration of Study Intervention

The study intervention is complete once the patient receives perflutren-enhanced US (see Study Schema). We anticipate that CEUS imaging will last approximately 15 minutes for each subject, including set-up, pre-scan, and image capture. The patient may be withdrawn from the study prior to this point if any of the following apply:

- Inter-current illness prevents completion of perflutren-enhanced US
- Unacceptable adverse event(s) prevents completion of perflutren-enhanced US
- Patient decides to withdraw from the study, **OR**
- General or specific changes in the patient's condition render the patient unacceptable for completion of perflutren-enhanced US in the judgment of the investigator.

#### 4.5 Duration of Follow Up

Patients will be followed up via review of their medical records and through receipt of 6-month and 1-year urinalysis and serum creatinine and a 1-year follow-up non-

contrast US. Additional imaging studies and histopathological diagnoses will also be obtained for any scheduled biopsy and/or surgery as dictated by standard of care. Patients will also be followed indefinitely after the initial year for lesion changes/histologic diagnosis or changes in kidney function.

#### 4.6 Removal of Patients from Protocol

Patients will be removed from study when any of the criteria listed in Section 4.4 apply. The Principal Investigator will be notified, and the reason for study removal and the date the patient was removed documented in the study documentation sheets. The patient should be followed-up per protocol.

#### **5.0 DRUG INFORMATION**

#### 5.1 Perflutren Lipid Microspheres (Lantheus Medical Imaging)

The Definity® vial contains components that upon activation yield perflutren lipid microspheres composed of octafluoropropane. Perflutren is a diagnostic drug that is intended to be used for contrast enhancement. The vial contains a clear, colorless, sterile, non-pyrogenic, hypertonic solution which is activated by mechanical agitation with Vialmix®.

Vialmix® is the activation device used in the preparation of US contrast imaging agents, including Definity®. Prior to activation, each Definity® vial contains 6.52 mg/mL octafluoropropane in the headspace and 0.75 mg lipid blend (0.045 mg DPPA, 0.401 mg DPPC, and 0.304 mg MPEG5000 DPPE), 103.5 mg propylene glycol, 126.2 mg glycerin, 2.34 mg sodium phosphate monobasic monohydrate, 2.16 mg sodium phosphate dibasic heptahydrate and 4.87 mg sodium chloride in water in the clear liquid. Upon activation, each mL of the milky white suspension contains a maximum of  $1.2 \times 10^{10}$  perflutren lipid microspheres with approximately 150 µL/mL octafluoropropane.

#### 5.2 Supplier/How Supplied

Perflutren (Definity®) will be provided to study subjects at no cost. Perflutren is supplied as a single use 2mL clear glass vial containing clear liquid. Each package contains 4 single-use vials.

#### 5.3 Handling and Dispensing of Perflutren

Perflutren lipid must be dispensed only from official study sites by authorized personnel according to local regulations. Perflutren should be stored in a secure area according to local regulations. It is the responsibility of the Investigator to ensure that study drug is only dispensed to study patients.

#### 5.4 Storage Requirements/Stability

The drug product should be stored in a secure location with limited access under controlled temperature conditions of 2-8° C (36° -46° F) in a refrigerator.

PI: [name] July 29, 2016

#### **5.5 Preparation**

See http://www.definityimaging.com/pdf/VIALMIX%20Users%20Guide.pdf, and the package insert for instructions on the use of Vialmix®.

#### 5.6 Dosage and Administration

See Section 4.2.4.

#### 5.7 Clinical Safety Summary

See prescribing information on perflutren when used according to its FDA indication (http://www.accessdata.fda.gov/scripts/cder/drugsatfda/ and highlights for perflutren prescribing at http://www.accessdata.fda.gov/drugsatfda\_docs/label/2011/021064s011lbl.pdf),

In addition, the following warnings and precautions are noted in the October 2011 labeling:

#### Serious Cardiopulmonary Reactions

Serious cardiopulmonary reactions including fatalities have occurred uncommonly during or shortly following perflutren-containing microsphere administration, typically within 30 minutes of administration. The risk for these reactions may be increased among patients with unstable cardiopulmonary conditions (acute myocardial infarction, acute coronary artery syndromes, worsening or unstable congestive heart failure, or serious ventricular arrhythmias). Always have cardiopulmonary resuscitation personnel and equipment readily available prior to perflutren administration and monitor all patients for acute reactions. The reported reactions include: fatal cardiac or respiratory arrest, shock, syncope, symptomatic arrhythmias (atrial fibrillation, tachycardia, bradycardia, supraventricular tachycardia, ventricular fibrillation, ventricular tachycardia), hypertension, hypotension, dyspnea, hypoxia, chest pain, respiratory distress, stridor, wheezing, loss of consciousness, and convulsions.

#### Anaphylactoid Reactions

In postmarketing use, uncommon but serious anaphylactoid reactions were observed during or shortly following perflutren-containing microsphere administration including: shock, hypersensitivity, bronchospasm, throat tightness, angioedema, edema (pharyngeal, palatal, mouth, peripheral, localized), swelling (face, eye, lip, tongue, upper airway), facial hypoesthesia, rash, urticaria, pruritus, flushing, and erythema. These have occurred in patients with no prior exposure to perflutren-containing microsphere products.

Systemic Embolization of Perflutren in Patients with Cardiac Shunts In patients with right-to-left, bi-directional, or transient right-to-left cardiac shunts phospholipid-encapsulated microspheres can bypass the pulmonary particlefiltering mechanisms and directly enter the arterial circulation resulting in

#### CONFIDENTIAL UNIVERSITY OF NORTH CAROLINA

microvascular occlusion and ischemia. In an animal study utilizing intra-arterial administration of activated perflutren, microsphere trapping was seen in small arterioles <15  $\mu$ m, especially at branch points and in capillaries at all doses tested, including doses directly applicable to those used in humans. An animal study utilizing intravenous administration did not result in arterial microvascular obstruction presumably because of filtering by the lungs. Do not administer perflutren by intra-arterial injection.

#### High Ultrasound Mechanical Index

High ultrasound mechanical index values may cause microsphere cavitation or rupture and lead to ventricular arrhythmias. Additionally, end-systolic triggering with high mechanical indices has been reported to cause ventricular arrhythmias. The safety of activated perflutren at mechanical indices greater than 0.8 has not been evaluated.

#### QTc Prolongation

ECG parameters for doses up to10  $\mu$ L/kg were monitored in 221 subjects at multiple time points from 1 hour to 72 hours after the first bolus injection. In the 221 subjects, QTc prolongations of >30 msec were noted in 64 (29%) subjects. Forty-six out of 64 subjects with QTc prolongations were further evaluated and 39% (18/46) showed associated cardiac rhythm changes. The effects of concomitant drugs were not studied.

#### 5.8 Return and Retention of Study Drug

Remaining reagent at the completion of the study or expired reagent will be destroyed by UNC IDS.

#### 6.0 EVALUATIONS AND ASSESSMENTS

#### 6.1 Pre-Study Assessments

Written informed consent will be obtained from the subjects prior to the implementation of any study procedures. The subject will receive a signed and dated informed consent form. A complete medical history will be taken at enrollment and reviewed on presentation for the study ultrasound. A serum or urine  $\beta$ -HCG test will be performed within 24 hours prior to perflutren administration if clinically appropriate. All medications (prescription and over-the-counter) taken within 24 hours prior to perflutren lipid administration will be recorded.

#### 6.2 Treatment Assessments

Subjects will be monitored for any untoward medical occurrences or toxicities from the time of signed informed consent through 30 minutes after perflutren lipid administration.

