#### 4.3 Follow-up

For all patients, the treatment path will be decided by the subject's primary physician. We will review the medical records from each patient for a minimum of 12 months post CEUS and document results of 6-month and 1-year urinalysis and serum creatinine and follow-up non-contrasted US 12 months after CEUS. Additionally, any contrast-enhanced or non-contrast CT and/or MRI findings or surgical procedures performed as part of their routine standard of care will be collected and reviewed.

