#### CONFIDENTIAL UNIVERSITY OF NORTH CAROLINA

#### 6.3 Follow-up Assessments

All post-CEUS clinical diagnoses based on 1-year follow-up non-contrasted US will be reviewed. Any post-operative histopathological diagnoses for patients who undergo biopsy/surgery within the 12-month follow-up period post perflutren lipid administration will be reviewed. Any additional non-contrasted or contrasted imaging (CT or MRI) within the 12-month follow-up period post perflutren lipid administration will be reviewed.

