#### 7.2 Documentation of non-serious AEs or SARs

For non-serious AEs or SARs, documentation must begin from day 1 of study treatment and continue through 24 hours after treatment is discontinued.

Collected information should be recorded in the Case Report Forms (CRF) for that patient. A description of the event, its severity or toxicity grade, onset and resolved dates (if applicable), and the relationship to the study drug will be documented.

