#### 7.3 SAEs or Serious SARs

#### 7.3.1 Timing

For any experience or condition that meets the definition of an SAE or a serious SAR, recording of the event must begin from day 1 of study treatment and continue through the 30-day follow-up period after treatment is discontinued.

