#### Time and Events Table

	Screening	Pre-CEUS Visit	CEUS study	Mo6 (Wk 24)	Mo12 (Wk 48)	Early Termination 
Inclusion/	Х					
Exclusion Criteria						
Comprehensive Medical History	X 	X 				
Informed Consent	X 	X 				
Education of potential side effects		х				
Pregnancy test (urine), if applicable		$X^4$				
Serum creatinine	Х			X 	X 	X 
Urinalysis		X 		X	X	
Contrast-Enhanced US (CEUS)			X 			
AE Assessment			X 			
Request tissue diagnosis				X9	X 	
Obtain follow-up						
conventional US and any					x	x
other imaging studies					^	~
obtained during the						

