#### CONFIDENTIAL UNIVERSITY OF NORTH CAROLINA

follow-up period					
Patients declining CEUS but allowing creatinine follow-up 					
Serum creatinine	Х		Х	Х	Х

For any patients that do not complete the CEUS study, an ongoing adverse events/serious adverse events will be followed to the resolution of the event. For any patient that is deceased before the 1-year follow-up most recent creatinine levels and imaging studies will be collected and autopsy results documented, if available.

Comprehensive medical history obtained at time of enrollment; thereafter history focused on symptoms and assessments.

Consent can be obtained and signed at either screening visit or during the prestudy visit. It will always be reviewed at pre-study visit, even if signed during screening visit.

Women of childbearing potential must have negative urine or serum pregnancy test on the day of CEUS study, prior to the study.

Serum creatinine levels will be obtained clinically at the discretion of the patient's primary provider. We will obtain results of serum creatinine levels drawn by the primary provider.

Urinalysis will be obtained prior to and post CEUS study. This will be obtained by Radiology Nursing staff as per agreement. Results will be obtained and recorded by Study Coordinator. At approximate 6 and 12-month intervals, urinalysis will also be obtained. This can be done locally with results sent to UNC.

During the CEUS study, Study Coordinator will record time of injection.

Adverse event assessment will happen during the CEUS study and the 30-minute post-study monitoring period, where they will be monitored by the Radiology nursing staff with vital signs (blood pressure and heart rate) recorded in the hospital's electronic monitoring system. These results will be collected by the Study Coordinator and documented in the Monitoring Logs/Flowsheets housed in the Radiology Research Coordinator Office.

For patients who undergo biopsy or nephrectomy, tissue diagnosis will be requested after the procedure.

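### Adverse-event assessment is scheduled only to 30 minutes after CEUS, so the rest of the 24-hour and 30-day recording windows has no AE-directed contact or chart check

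*Combined protocol and SAP*

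**What the plan says.** Scheduled AE assessment:

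- Section 6.2 monitors subjects "from the time of signed informed consent through 30 minutes after perflutren lipid administration".
- Appendix 2 marks AE assessment once, in the CEUS column. Its footnote 8 reads: "Adverse event assessment will happen during the CEUS study and the 30-minute post-study monitoring period".
- Section 4.2.4 has nursing staff observe the patient for that half hour, with blood pressure and heart rate at 15 and 30 minutes.

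Recording windows:

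- Section 7.2, for non-serious events: "documentation must begin from day 1 of study treatment and continue through 24 hours after treatment is discontinued".
- Section 7.3.1, for serious events: recording must "continue through the 30-day follow-up period after treatment is discontinued".
- Section 7.3.2 gives 24 hours to record a serious event, counted from when the team learns of it.

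Later follow-up:

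- Section 4.3 provides for record review over at least 12 months, to "document results of 6-month and 1-year urinalysis and serum creatinine and follow-up non-contrasted US 12 months after CEUS", together with CT/MRI findings and surgical procedures.
- Section 6.3 lists the diagnosis from the one-year ultrasound, histology, and "Any additional non-contrasted or contrasted imaging (CT or MRI) within the 12-month follow-up period".
- Sections 6.4 and 7.4.1 follow creatinine and urinalysis. Section 6.4 adds a comparison group of patients who decline CEUS.
- Appendix 2, footnote 1, covers patients who "do not complete the CEUS study, an ongoing adverse events/serious adverse events will be followed to the resolution of the event".
- Appendix 2 also has a pre-CEUS row, "Education of potential side effects", whose content is not described.

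**The concern.** The protocol sets two recording duties that outlast its only scheduled AE assessment. Staff who follow the schedule exactly would learn of an event starting after discharge only if the patient or a provider volunteers it, or if it turns up in a chart opened for another purpose. A blank AE record after the first half hour could then mean that nothing happened or that nobody asked.

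What is at stake is the completeness and timeliness of the safety record. The study-wide hold in 7.4.3 and the reporting duties in 7.3.3 can act only on events the team knows about. The protocol's own background gives some reason to look later. In the pre-market trials described in 1.3.2, 19 subjects had serious cardiopulmonary events. Eight died several days after dosing, and the other 11 events appeared at 2-15 days. The protocol attributes these mainly to underlying disease but leaves open a contribution from the drug.

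**Working it through.** The plan gives no figure on this point to reproduce. The check sets the windows against the schedule and then sizes the effect.

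**Windows against schedule**

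| Period after CEUS | Recording required | Scheduled AE step |
|---|---|---|
| 0 to 30 minutes | Non-serious and serious | Yes: bedside monitoring |
| 30 minutes to 24 hours | Non-serious and serious | None |
| 24 hours to day 30 | Serious | None |

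The next time point in Appendix 2 is Week 24: 24 x 7 = day 168, which is 168 - 30 = 138 days after the serious-event window closes. It carries creatinine, urinalysis and a request for tissue diagnosis, but no AE item. A post-CEUS urinalysis is also scheduled (6.4, 7.4.1), but it is aimed at hematuria.

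Section by section, the later reviews name laboratory results, imaging, histology and surgery. None names adverse events, and none is timed to 24 hours or 30 days. Footnote 1 covers only ongoing events in patients who do not complete CEUS.

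**Expected numbers in the 75 patients of 8.2**

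- Serious events at the post-marketing rate cited in 1.3.2 (1-3 per 10,000): 75 x 0.0001 = 0.0075 and 75 x 0.0003 = 0.0225, or about 0.008-0.023.
- Serious cardiopulmonary events at the pre-market rate: 75 x 19/1716 = 0.83 patients. This is not a drug-related rate: the protocol judges these events mostly underlying disease, and this study excludes several high-risk cardiac and pulmonary conditions.
- Any treatment-related reaction at the pre-market rate: 75 x 144/1716 = 6.3 patients. The share starting after 30 minutes is not given, so late reactions lie between 0 and 6.3. The onset times reported for the discontinued patients, 1-15 minutes, point to the low end.

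**Pharmacology**

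Section 1.3.2 gives a mean half-life of 1.3 minutes, from eight healthy subjects. Thirty minutes is 30/1.3 = about 23 half-lives, which supports the half hour as the main period of acute risk.

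**Work added by two contacts per patient**

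2 x 75 = 150 contacts. At an assumed 10 minutes each, 1,500 minutes = 25 hours; at 5 to 20 minutes each, 12.5 to 50 hours.

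**The case against.** The strongest case against is that the plan already watches the period that matters. The agent clears within minutes, the label information says most serious cardiopulmonary reactions come in the first half hour, and nurses observe every patient for that time. Charts are reviewed for at least a year, records can be obtained directly from providers (7.4.1), and 6.4 makes every dosed patient evaluable for toxicity. The UNC team meets every two weeks and both sites confer at least monthly (7.4), and an outside Medical Monitor is to be asked for a review (7.4.4). Section 7.1.1 also excludes disease progression not attributed to study therapy, so some events like the pre-market ones might not be recordable. Reporting instructions may sit in the consent form, whose pages are not available for review.

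Much of this stands, and it is why the point is small. It does not close the gap. Meetings and a Medical Monitor assess known events; neither is described as seeking new ones. Chart review could reveal a hospitalization, but its stated content is not AEs and its timing is not tied to either window. Attribution under 7.1.1 can be judged only once the event is known.

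Three stronger readings are tempting, and the documents do not support them:

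- A reader might infer that 6.2 contradicts 7.2 and 7.3.1. It does not: 6.2 concerns monitoring, the other two concern documentation, and all can be followed together.
- A reader might infer that the two windows have no assessment behind them at all. Their first 30 minutes is actively monitored.
- A reader might infer that a late-found event would let many more patients be dosed before a hold. The documents give no discovery times, so any such count rests on assumed days and on an event that is very unlikely at the cited rate.

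**Conclusion.** The point holds as a low-cost safety improvement. After the first half hour, neither recording window has an AE-directed step, so later events could be missed or found late.

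The expected impact is small: 0.008-0.023 serious events among 75 patients, assuming that the cited rate of 1-3 per 10,000 carries over to patients with kidney disease and that all 75 are dosed. The share of events starting after 30 minutes is unknown and probably low. The sensitivity and specificity estimates do not depend on AE capture and are unaffected. No conclusion is drawn about the consent form.

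**What to change.** Keep the 30-minute bedside monitoring. Add two rows to Appendix 2, applying at both UNC and the affiliate and to every dosed subject, including any healthy volunteers given perflutren:

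1. a coordinator call at about 24 hours, asking about new symptoms;
2. a call or AE-directed chart check at day 30, asking about hospitalizations and other serious events.

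Refer to both steps in 6.2. Use the existing pre-CEUS education step to tell patients to report symptoms to 24 hours and any hospitalization to 30 days.

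The cost is about 150 brief contacts by existing coordinators, roughly 25 staff hours at the assumed 10 minutes each. It would be higher where outside records must be requested or volunteers are dosed; the protocol does not say how many volunteers there will be. The change also needs an amendment approved by the IRB (9.5). It adds no new patient procedure.

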#### CONFIDENTIAL UNIVERSITY OF NORTH CAROLINA

#### 6.3 Follow-up Assessments

All post-CEUS clinical diagnoses based on 1-year follow-up non-contrasted US will be reviewed. Any post-operative histopathological diagnoses for patients who undergo biopsy/surgery within the 12-month follow-up period post perflutren lipid administration will be reviewed. Any additional non-contrasted or contrasted imaging (CT or MRI) within the 12-month follow-up period post perflutren lipid administration will be reviewed.

#### 6.4 Assessment of Safety

Any patient in whom perflutren administration is initiated will be evaluable for toxicity.

Baseline creatinine (within 8 weeks prior to study) and urinalysis (on day of study, pre and post-CEUS) will be collected from each patient prior to CEUS. At 6-month and 1-year post-CEUS, serum creatinine levels and urinalysis will be obtained from primary providers. Serum creatinine from a comparison group drawn from patients who meet study inclusion and exclusion criteria but decline to participate in the study will be followed over the study period to detect potential adverse effects the study intervention may have on kidney function of the study subjects. Their serum creatinine values will be collected at 6-month and 1-year post initial recruitment with a minimum of 1 value at 1-year timepoint.

#### 6.5 Tissue Collection and Optional Storage

If a patient undergoes nephrectomy, all nephrectomy specimens will be collected by the tissue procurement facility. Final diagnoses will be obtained by chart review.

#### 7.0 ADVERSE EVENTS

#### 7.1 Definitions

#### 7.1.1 Adverse Event (AE)

An adverse event (AE) is any untoward medical occurrence (e.g., an abnormal laboratory finding, symptom, or disease temporally associated with the use of a drug) in a patient or clinical investigation subject administered a pharmaceutical product and which does not necessarily have a causal relationship with this treatment. An AE can therefore be any unfavorable and unintended sign (including an abnormal laboratory finding), symptom, or disease temporally associated with the use of a medicinal product, whether or not related to the medicinal product. Each AE will be graded on a mild-moderate-severe scale.

Hospitalization for elective surgery or routine clinical procedures that are not the result of an AE (e.g., surgical insertion of central line) need not be considered AEs and should not be recorded as an AE. Disease progression should not be recorded as an AE, unless it is attributable by the investigator to the study therapy.

